#### 9.5 Monitoring

The study team will review all adverse events during the study by cumulative reports, on a monthly basis. Adverse events will be graded using the ACTG toxicity grading scale and recorded using standard AE electronic data capture. The study investigators will monitor safety events in aggregate on monthly team calls. An independent Data Safety and Monitoring Board will not be used for this study.

#### 9.6 Analyses

This section briefly describes the planned statistical analysis. The Statistical Analysis Plan (SAP), which will be finalized prior to database lock, provides further details. In case the language in this section differs from the language in the SAP, the SAP takes precedence.

In general, analyses will incorporate the modified intent-to-treat principle, namely, all randomized participants dispensed at least one dose of medication will be included in the analysis. No adjustments for multiple comparisons will be made for secondary analyses, and a p-value of 0.05 will be considered statistically significant.

Demographic data, concomitant medications, site of TB infection, adverse events prior to entry into study due to TB medications and past medical history will be collated and described for all study subjects and presented in aggregate for phase 1 and by randomized group for phase 2.

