### 3.5.1 Intervention Group

[figure not shown]
In intervention subjects, the patch monitor will be changed weekly by the subject themselves or under the supervision of the AVRC/County healthcare worker if requested. Subjects will be contacted weekly for review of side effects and any questions by AVRC and will be able to contact the AVRC and County healthcare worker at any time with questions regarding the intervention. Subjects will continue to be followed by County healthcare per their usual routine (i.e., County nurse visit once a week, physician visit once a month, and County outreach worker visits as directed by County nurse). All phone calls between the subject and the AVRC or County healthcare workers including medical information, such as physical symptoms possibly associated with side effects or other medical complaints, will be recorded as per the Schedule of Events (see Section 6) and communicated to PHS, OCHCA, or the physician with primary responsibility for the subject's TB treatment. All phone calls between the subject and the AVRC or County healthcare workers related to the function of the DHFS, will be directed to and dealt with by the AVRC in conjunction with PDH personnel.

The AVRC study coordinator and County healthcare worker will review the subject ingestion log on the PDH website daily on business days to record the subject's wirelessly confirmed dosing. This follows current County practices. The wirelessly confirmed dose will be entered by AVRC study staff into the study database via a secure user-authenticated website designed and hosted by the UCSD Center for AIDS Research Bioinformatics and Information Technologies (BIT) Core. The identity of staff recording the wirelessly confirmed dose will be recorded in the study database as the user who logged into the secure website to enter the data. The County healthcare worker will enter the subject's wirelessly confirmed dosing into the County medical records daily, following current County practices. Each site should check daily to see that the subject's data has

been recorded properly into the study database (by the AVRC) and medical record (by PHS or OCHCA).

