## 9.0 STATISTICAL CONSIDERATIONS

### 9.1 General Design Issues

This study is a prospective, two phase, open-label feasibility study with lead in (Phase 1) and randomized (Phase 2) components to evaluate the utility of the DHFS for monitoring TB treatment. In the first phase, all subjects will receive DHFS IS-RM (or Rifamate with co-ingestion of an encapsulated edible sensor) and a series of doses will be witnessed in order to determine the detection accuracy of the system as well as to evaluate subject acceptance and ability to use the system. In the randomized phase, those randomized to intervention will continue to use the DHFS IS-RM and control subjects will receive SOC DOT.

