#### Phase 2 (Percentage of Witnessed Doses)

A mixed effects regression model will be used to determine if the WOT intervention arm will produce greater percentage of witnessed doses compared to the DOT standard of care arm at treatment end. This model will include time, treatment arm, and time-by-treatment arm interaction terms. In addition, any covariates, which are simultaneously unbalanced at baseline and associated with the outcome, will be included in the model. Time will be treated as a categorical variable. A significant treatment effect will be concluded if the p-value for the time-by-treatment interaction contrast in the model is  $\leq 0.05$ . Permutation tests may be implemented to verify that valid p-values will be obtained even if model assumptions are not correct. Note that the linear mixed model seamlessly accommodates different times of measurement as well as missed measurements and data from subjects who are lost to follow-up. Generalized estimating equation (GEE) models will be used as the sensitivity analysis method.

Note that when considering percentages of witnessed doses over the entire study period in aggregate, this model reduces to a multiple linear regression, and the independent variable of interest is the treatment arm.

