#### 11.1.6 Retrieval

OCCAMS provides methods for both viewing and downloading data collected through eCRFs on a form-by-form basis. Files can be downloaded in csv format, which can then be easily imported into standard statistical packages (R, SAS, etc.) for offline analysis. By default, data viewing and download permissions are restricted to investigator and analyst roles, but can be expanded to others as needed. Regarding specimen retrieval, the `occams.lab` module provides query functionality allowing specimen search by type, date, and PID, as well as a specimen inventory system that supports the tracking of specimens using computer-generated barcoded labels.

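### The SAP may be settled at any time up to database lock and may override the Phase 2 primary analysis, in an open-label trial with no described masking of outcomes by arm and an ambiguous primary test

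*Combined protocol and SAP*

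**What the plan says.** On timing, section 9.6 states: "The Statistical Analysis Plan (SAP), which will be finalized prior to database lock, provides further details". Database lock is the latest permitted date, and no earlier milestone is set. On authority, the same paragraph continues: "In case the language in this section differs from the language in the SAP, the SAP takes precedence". What can be overridden is therefore everything in 9.6: the modified intent-to-treat population, the Phase 2 mixed model, its 0.05 decision rule and its covariate rule.

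On blinding, section 9.1 opens: "This study is a prospective, two phase, open-label feasibility study with lead in (Phase 1) and randomized (Phase 2) components". On data flow, section 3.5.1 says of the intervention arm: "The AVRC study coordinator and County healthcare worker will review the subject ingestion log on the PDH website daily on business days", and study staff enter those confirmed doses into the study database. Section 3.5.2 has the control arm's prescribed and witnessed doses taken from County records into the same database. Section 11.1.6 says that by default "data viewing and download permissions are restricted to investigator and analyst roles". It sets no limit by arm and none that lasts until lock.

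On the test, section 9.6.1 concludes a treatment effect from the p-value of the time-by-treatment interaction contrast. It then notes that, for whole-period percentages taken in aggregate, "this model reduces to a multiple linear regression, and the independent variable of interest is the treatment arm". Section 9.4 states the Phase 2 aim as the percentage over the entire study period, compared between arms, and sizes the trial on a two-sample t-test.

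**The concern.** Signing a SAP just before lock protects the error rate when those who write it cannot see outcomes by arm. Here allocation is known, subject-level doses accumulate in a database open to investigator and analyst roles, and the document describes neither a blinded statistician nor a blinded data review. Section 9.5 also rules out an independent board.

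The SAP has real work to do. It must say which contrast is primary. It must also say which covariates enter the model, because 9.6.1 admits any that are unbalanced at baseline and related to outcome, with no list or threshold. If those points are settled by someone who has seen results by arm, the two-sided 0.05 level used in 9.4 no longer describes the test, and a reader of the final report could not tell whether that had happened.

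**Working it through.** **1. The plan's own figure.** Inputs from section 9.4: 50 v 25 subjects, difference 5 points, SD 6 points, two-sided alpha 0.05.

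- Standard error = 6 × √(1/50 + 1/25) = 6 × √0.06 = 1.470.
- Standardised difference = 5 / 1.470 = 3.402.
- Normal approximation: Φ(3.402 − 1.960) = Φ(1.442) = 92.5%.
- Noncentral t on 73 degrees of freedom: 91.9%.

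The stated 92% reproduces. It belongs to the arm difference in whole-period percentage, so the sizing is not in dispute.

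**2. Can the two tests in 9.6.1 disagree?** Read the interaction contrast as (arm difference at end) − (arm difference at Week 4). Section 9.6.1 does not define the contrast, so this is one reading. If the 5-point difference is constant over time, the contrast has expectation 5 − 5 = 0 and its power equals alpha. Simulation (20,000 trials per setting, normal data, SD 6, equal correlation ρ between Week 4, Week 8 and end) gave 4.8% to 5.2% for the contrast and 91.5% to 92.0% for the arm difference at end. The choice can reverse the conclusion.

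**3. Null rejection rate if the better of the two is reported.** Under equal correlation ρ the two test statistics correlate at √((1 − ρ)/2). No value of ρ is given in the documents, so a range is shown.

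| Assumed ρ | Correlation of the two tests | End difference alone | Contrast alone | Better of the two |
|---|---|---|---|---|
| 0.3 | √0.35 = 0.59 | 5.2% | 5.2% | 9.1% |
| 0.5 | √0.25 = 0.50 | 4.9% | 5.0% | 8.9% |
| 0.7 | √0.15 = 0.39 | 5.1% | 4.9% | 9.3% |
| 0.9 | √0.05 = 0.22 | 4.9% | 5.1% | 9.5% |

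For reference, two independent 5% tests give 1 − 0.95² = 9.75%, which is why the range is narrow.

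A second simulation used beta-distributed adherence: mean 92%, SD 6 points, later drift SD 4 points, five doses a week in both arms, Phase 2 length 4 to 26 weeks, 6,000 trials. It gave 5.2% and 5.1% singly and 9.9% for the better of the two, with Monte Carlo error √(0.099 × 0.901 / 6,000) = 0.4 points. A repeat on those inputs gave 9.6%.

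**4. The other reading.** Section 9.2.1 defines the endpoint cumulatively from Phase 2 Day 0, so the end-of-study value is the whole-period percentage. Section 9.6.1 asks about the difference at treatment end. If the contrast is meant as the arm difference at that point, the two tests are essentially one test. The better-of-two rate on the inputs of the second simulation is then 5.1%: no inflation.

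**The case against.** Finalising before lock is ordinary practice, and the separate SAP is not in the supplied document. It may have been signed before any Phase 2 outcome existed. A reader might infer that the results will be known when the test is chosen, or that the test was in fact chosen that way. The documents support neither. Section 3.5.1 describes subject-level log review, which is needed to contact subjects about unconfirmed doses. Section 3.5.2 gives no timing for entry of control-arm doses. Section 9.5 reviews safety in aggregate, and the monthly reports in 11.2.1 list screening, early terminations, late visits, adverse events and data quality. No tabulation of witnessed doses by arm is planned. Results by arm are knowable, not scheduled to be known.

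The precedence sentence is also limited to 9.6. The endpoint definition (9.2.1) and the stated aim (9.4) lie outside it.

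A reader might also infer larger inflation. Adding a rank test and a Week 8 comparison gives 11.4% and then 13.1%. Adding Weeks 4 and 8 to the two tests gives 12.6% to 16.4%. Section 9.6.1 names none of these as a primary test, so those figures should not be charged to the plan.

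The simulation inputs are partly invented. Five doses a week in both arms is simpler than daily dosing with the sensor (5.2.1) against DOT two, three or five times a week (3.5.3), and Phase 2 may run longer than 26 weeks.

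Finally, this is a pilot. That lowers the stakes but does not remove the point, since 9.6.1 sets a significance rule and 9.4 ties the effect size to prompting further study.

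What stands is the open date, the unrestricted override of the primary analysis within 9.6, the absence of described masking, and the ambiguity in 9.6.1.

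**Conclusion.** The point holds as an opportunity for a data-informed choice. The worst case from the two tests in 9.6.1 is a null rejection rate of about 9% to 10% instead of 5%. That figure requires three things: the contrast is read as change from Week 4 to end, the better p-value is reported, and the assumed adherence and correlation values are roughly right. Under the treatment-end reading this pair adds nothing. Freedom over covariates would add to the opening but has not been quantified. The 92% power is unaffected. This is a cheap safeguard that should be adopted. It is not a defect that invalidates the trial, and it makes no allegation about what was done.

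**What to change.** Revise section 9.6, and 9.6.1 with it, in one amendment.

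1. Replace the database-lock deadline with a requirement that the SAP be signed and dated before any tabulation or analysis of witnessed doses by arm. Hold exports of outcomes by arm for analysis until then. Daily subject-level adherence review continues unchanged.
2. Name one Phase 2 primary test consistent with 9.4: the arm difference in percentage of witnessed doses from Phase 2 Day 0 to end of study, in the modified intent-to-treat population that 9.6 already defines. Without this step, protecting the present wording of 9.6.1 would only lock in its ambiguity.
3. Limit the precedence sentence. Once data by arm have been seen, any change to the primary endpoint, population or test needs a dated amendment stating who had seen them, and is reported as post hoc. The SAP may keep precedence on other detail.

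The cost is a few sentences, earlier SAP sign-off and less freedom to alter the primary analysis late. No extra subjects or data are needed.

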### 9.6.1 Analysis for Primary Outcomes

#### Phase 1 (Detection Accuracy of the DHFS)

The primary analysis of the positive detection accuracy will be done by calculating the number of correct sensor detected IS-RM (or Rifamate with co-ingestion of an encapsulated edible sensor) ingestions divided by the total number of actual witnessed ingestion events with a 95% confidence interval. The data will be reviewed to detect false positive events (recorded ingestion when none should have occurred), especially on days where an observed dose is given and ingestion was recorded at another time. False positive and false negative ingestions will be determined as well as true positive ingestions. An intent-to-treat (all inclusive analysis) will be done that includes all events but will exclude doses that were either known to be not ingested or ingested during the period of time when the patch was known not to be worn. An additional adjusted analysis will use the same definition, but will exclude doses that were taken during a time period when the patch was not functioning properly, either by malfunction or user error.

#### Phase 2 (Percentage of Witnessed Doses)

A mixed effects regression model will be used to determine if the WOT intervention arm will produce greater percentage of witnessed doses compared to the DOT standard of care arm at treatment end. This model will include time, treatment arm, and time-by-treatment arm interaction terms. In addition, any covariates, which are simultaneously unbalanced at baseline and associated with the outcome, will be included in the model. Time will be treated as a categorical variable. A significant treatment effect will be concluded if the p-value for the time-by-treatment interaction contrast in the model is  $\leq 0.05$ . Permutation tests may be implemented to verify that valid p-values will be obtained even if model assumptions are not correct. Note that the linear mixed model seamlessly accommodates different times of measurement as well as missed measurements and data from subjects who are lost to follow-up. Generalized estimating equation (GEE) models will be used as the sensitivity analysis method.

Note that when considering percentages of witnessed doses over the entire study period in aggregate, this model reduces to a multiple linear regression, and the independent variable of interest is the treatment arm.

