## 9.3 Randomization

Subjects will be randomized 2:1 to DHFS or SOC. Randomization will be done centrally via the study database.

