## 9.4 Sample Size and Accrual

Phase 1: For phase 1, both groups will use the DHFS for 2 weeks, and we will estimate the confidence interval around an estimate of the detection accuracy of the DHFS by taking the ratio of the sensor-enabled ingestion recorded events compared to the witnessed doses. Assuming that each of 75 subjects completes 2 weeks of DHFS dosing and has a total of three witnessed doses each week (a total of 450 dosing events) and that the overall rate of positive detection is 95%, then the 95% confidence interval around the point estimate of 95% accurate detection would be  $\pm 2.0\%$ . If the detection accuracy was 97%, then the 95% confidence interval around the point estimate of 97% accurate detection would be  $\pm 1.6\%$ .

Phase 2: The primary aim of phase 2 is to assess the percentage of prescribed witnessed doses completed over the entire study period for each subject and to compare the DHFS arm to the DOT arm. This metric captures the persistent efficacy of the DHFS ingestion sensor system and allows comparison to SOC DOT of varying intervals (5 times, 3 times, or 2 times per week that may occur in the SOC). Sample size calculations were based on a two-sided, two-sample t-test to compare the differences in adherence percentages by treatment arm using different mean/standard deviation scenarios. Calculations were performed using the R statistical package (version 2.14.0) ([www.r-project.org](http://www.r-project.org)).

In choosing a sample size for this pilot study, we considered issues of cost, feasibility, as well as how large an effect size would be of interest to spur further study of this intervention in this population. Assuming a two-sided alpha of 0.05, an adherence percentage in the DOT arm of 90%, and a common standard deviation of 6%, we will need 75 participants (50 DHFS arm and 25 DOT arm) to detect a 5% difference (i.e. 95% adherence percentage in DHFS arm) with 92% power.

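### The Phase 2 primary model chooses its covariates after outcomes are seen; a short list of pre-randomisation covariates fixed in advance would be a cheap improvement

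*Combined protocol and SAP*

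**What the plan says.** Section 9.6.1 (Phase 2) fixes three terms: "This model will include time, treatment arm, and time-by-treatment arm interaction terms". It then states that "any covariates, which are simultaneously unbalanced at baseline and associated with the outcome, will be included in the model". The decision rule follows: "A significant treatment effect will be concluded if the p-value for the time-by-treatment interaction contrast in the model is" at most 0.05. A closing note says that for the whole-period percentage "this model reduces to a multiple linear regression, and the independent variable of interest is the treatment arm".

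Section 9.3 names no stratification factor: "Subjects will be randomized 2:1 to DHFS or SOC. Randomization will be done centrally via the study database". No covariate is therefore tied to the design.

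Section 9.4 sizes the trial without adjustment: "Sample size calculations were based on a two-sided, two-sample t-test to compare the differences in adherence percentages by treatment arm".

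No section lists candidate covariates, says what counts as unbalanced or associated, or says whether association is judged with the arms pooled. Section 9.6 describes itself as brief and gives precedence to a SAP to be finalised before database lock. No separate SAP text is in the document supplied.

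**The concern.** Two things are at stake.

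- **When the model is fixed.** Association with the outcome cannot be judged without outcome data. The trial is open-label (Sections 3.0 and 9.1). Study staff read and enter the intervention arm's ingestion records on business days (Section 3.5.1). The pool of possible covariates is wide: demographics, comorbidities and concurrent medications (Section 3.3), site of infection and earlier adverse events (Section 9.6), and five questionnaires (Table 1). With 75 subjects some chance imbalances are expected, so the undefined criteria leave real room for choice.
- **Precision.** A covariate helps by removing outcome variance, and it does so whether or not it is balanced. A rule that also demands imbalance drops most prognostic variables and leaves their variance in the error term.

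**Working it through.** **Inputs.** Section 9.4 gives the design: "Assuming a two-sided alpha of 0.05, an adherence percentage in the DOT arm of 90%, and a common standard deviation of 6"%, and "we will need 75 participants (50 DHFS arm and 25 DOT arm) to detect a 5% difference", with 92% power. The number of candidates, their prognostic strength (R²) and the screening thresholds are not in the documents and are assumed below.

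**1. The plan's own figure.** Standard error = 6 × √(1/50 + 1/25) = 6 × 0.2449 = 1.470. Noncentrality = 5/1.470 = 3.40. On 73 degrees of freedom the critical value is 1.993 and the noncentral t gives 91.9%. The stated 92% is reproduced. At 4 points, noncentrality is 4/1.470 = 2.72 and power is about 77%.

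**2. Three prespecified covariates.** The residual SD becomes 6 × √(1 − R²), on 75 − 5 = 70 degrees of freedom (critical value 1.994). Chance imbalance in three covariates adds about 3/70 = 4% to the variance of the arm estimate.

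| R² | Residual SD | Power at 4 points | Power at 5 points |
|---|---|---|---|
| 0 | 6.00 | 75% | 91% |
| 0.1 | 5.69 | 79% | 93% |
| 0.2 | 5.37 | 84% | 96% |
| 0.3 | 5.02 | 88% | 98% |

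**3. The plan's rule, by simulation.** The model is the whole-period linear regression, 50 v 25, total SD 6, with 10 independent candidates of which 3 are prognostic. A covariate is kept only if its imbalance test and its outcome-association test both pass a common threshold between 0.05 and 0.20.

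| R² 0.2-0.3 | Plan's rule | Prognostic covariates prespecified |
|---|---|---|
| Type I error | 0.033-0.051 | about 0.05 |
| Power at 4 points | 75-78% | 84-89% |
| Power at 5 points | 90-92% | 95-98% |

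By the midpoints, the gap is about 86.5 − 76.5 = 10 points at a 4-point difference and 96.5 − 91 = 5.5 points at a 5-point difference. At R² = 0.1 prespecification gains about 1-6 points. At R² = 0 it loses about 1-3.

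**4. Sensitivity to the assumptions.** With 1, 5 or 10 candidates and R² of 0.3-0.5, the rule's power was 74-80% at 4 points and about 91-94.5% at 5. Its type I error was 0.027-0.048. With non-prognostic candidates, type I error stayed at about 0.05.

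**5. Which estimate this concerns.** A time-by-arm contrast compares within-subject changes between arms. A time-constant covariate entered as a main effect shifts all of a subject's values equally, so it cancels from that contrast. In random-intercept models with complete data at three times, adding a prognostic covariate left the interaction estimate identical and its p-value effectively unchanged (0.2049695 v 0.2049694). The figures above therefore apply to the arm difference at treatment end or over the whole period. That is the aim stated in Section 9.4 and the regression in the closing note of Section 9.6.1.

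**The case against.** **The rule does little harm on the plan's own terms.** This stands. At the planned 5 points its power is about the 92% that was designed for. The 4-point difference is not in the protocol, and unadjusted power there is about 77% anyway. What is lost is a gain that the plan could have had.

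**The comparator knows which covariates matter.** This is fair. Nothing in the documents shows that any named variable explains 20-30% of variance, so the gain is conditional. The loss if they explain nothing is small.

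**The SAP may settle it.** It may, and then Section 9.6.1 only needs to match it. That text is not available here. The optional permutation tests would protect the p-value only if covariate selection were repeated within each permutation, which is not stated. The GEE sensitivity analysis does not fix the covariate set.

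**Stronger readings that the documents do not support:**

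- A reader might infer that the rule inflates the false-positive rate. Applied as written at a fixed threshold, it is nominal to conservative. If an analyst reported the better of the unadjusted and selected models, the rate was about 0.050-0.065 in simulation, but nothing in the plan says this would be done.
- A reader might infer that adjustment happens mainly when it widens the standard error. In null runs where the rule adjusted, the standard error widened in only 27-40% of cases, and its mean ratio to the unadjusted one was 0.96-0.99. At 5 points it widened in 43-52%.
- A reader might infer that the literal time-by-treatment p-value loses power. With complete data and a main-effect covariate, it does not change.

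**Conclusion.** The point holds as a cheap improvement, not as a threat to validity. The rule leaves the primary model open until outcomes are seen and omits prognostic variables that happen to be balanced. For the arm difference at treatment end or over the whole period, it forgoes roughly 5 points of power at the planned difference and roughly 10 at 4 points. That size rests on assumed R² of 0.2-0.3, independent candidates, common thresholds of 0.05-0.20 and the aggregate regression form. It shrinks to about 1-6 points at R² = 0.1 and reverses to a small loss at R² = 0. The trial is not underpowered by the rule on its own assumptions.

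**What to change.** Replace the covariate sentence in Section 9.6.1, and any matching SAP text, with a short list fixed before any by-arm outcome summary. Include the listed variables whatever the observed balance, and report the unadjusted model as a sensitivity analysis.

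- **Eligible variables:** only those measured before randomisation and already collected. Examples are County (San Diego or Orange) and the Phase 1 Day 0 self-efficacy score, which Table 1 schedules. Sections 3.5.1 and 3.5.2 mention only the Phase 2 questionnaires, so confirm that the Phase 1 score is being captured.
- **Do not use the Phase 2 Day 0 self-efficacy score.** It is taken after open-label randomisation (Table 1, Section 6.2.2.1), and self-efficacy is itself compared between arms (Sections 1.1.7 and 1.2.9).
- **Use a Phase 1 adherence measure only if it is first defined and shown, with arms pooled, to vary.** Section 9.2.1 defines the percentage of witnessed doses only from Phase 2 Day 0. Completing Phase 1 requires four successful witnessed ingestions (Section 3.5), so values may sit near the ceiling.

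The cost is a few sentences, two or three degrees of freedom, and about 1-3 points of power if the covariates prove not to be prognostic.

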##### Phase 2 (1.2.2) Percentage of Witnessed Doses

This will be calculated as the total number of witnessed doses ingestions divided by the total number of prescribed witnessed dose ingestions. For the DHFS, witnessed doses by DHFS is defined as the total number of dose ingestions confirmed by DHFS, divided by the total number of prescribed witnessed dose ingestions for TB treatment. For SOC, witnessed doses will be defined as the total number of dose ingestions that are actually witnessed by a healthcare worker, divided by the total number of prescribed witnessed dose ingestions for TB treatment. This endpoint will be calculated from Phase 2, Day 0 to Weeks 4, 8 and end of study.

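### The Phase 2 decision rule rests on an undefined time-by-arm interaction contrast; read literally, it tests change in the arm gap, not the arm difference the trial was sized on

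*Combined protocol and SAP*

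**What the plan says.** Section 9.2.1 defines the Phase 2 primary endpoint as witnessed doses divided by prescribed witnessed doses, and adds: "This endpoint will be calculated from Phase 2, Day 0 to Weeks 4, 8 and end of study".

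Section 9.4 states the aim for sizing: "The primary aim of phase 2 is to assess the percentage of prescribed witnessed doses completed over the entire study period for each subject", with the DHFS arm then compared with the DOT arm. On method it says: "Sample size calculations were based on a two-sided, two-sample t-test to compare the differences in adherence percentages by treatment arm". With 50 and 25 subjects, a DOT mean of 90% and a common SD of 6%, the trial is said "to detect a 5% difference (i.e. 95% adherence percentage in DHFS arm) with 92% power".

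Section 9.6.1 (Phase 2) fits a mixed model with time, arm and their interaction, time being categorical. It makes three statements about the target:

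- The model is to show whether the DHFS arm has a "greater percentage of witnessed doses compared to the DOT standard of care arm at treatment end".
- The decision rule is: "A significant treatment effect will be concluded if the p-value for the time-by-treatment interaction contrast in the model is" at most 0.05.
- For the whole-period aggregate, the model becomes a linear regression in which "the independent variable of interest is the treatment arm".

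Section 9.6 adds: "In case the language in this section differs from the language in the SAP, the SAP takes precedence". The documents reviewed contain no SAP text that defines the contrast.

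**The concern.** An interaction can stand in for a treatment effect when the first time point is a pre-randomisation baseline, because the arms are then equal at the start by design. This endpoint has no such baseline. Its first value already covers four weeks of randomised treatment. With arm and categorical time both in the model, the interaction terms measure how the arm gap at Week 8 or end of study differs from the gap at Week 4. They do not measure the gap itself.

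Two analysts could therefore take the same data and this sentence and reach opposite conclusions. One, testing the arm difference at the end, would have the power stated in 9.4. The other, testing the interaction, would probably miss an advantage that appears early and holds. The second analyst could also declare an effect when an early difference has vanished by treatment end.

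Section 9.6.2 applies models analogous to the primary one to the secondary outcomes, so the same question arises wherever that model is used.

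**Working it through.** **Inputs from section 9.4:** n = 50 and 25, difference 5 points, SD 6, two-sided alpha 0.05.

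**Assumptions (not in the documents):** three time points (Week 4, Week 8, end of study), SD 6 at each, the same correlation ρ between any two time points with ρ = 0.5 or 0.8, normal data, and all 75 subjects observed at all three times.

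**1. The plan's own figure.** The noncentrality is 5 / (6 × √(1/50 + 1/25)) = 5 / (6 × 0.2449) = 3.40. With 73 df and critical value 1.993, noncentral-t power is **91.9%**. The stated 92% reproduces, and it belongs to an arm difference with one value per subject.

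**2. Literal interaction, last-minus-first contrast.** The within-subject change has SD 6 × √(2(1 − ρ)), which is 6.00 at ρ = 0.5 and 3.79 at ρ = 0.8. If the arm gap grows by g points, the noncentrality is g / (SD of change × 0.2449) on 73 df. Example: g = 2.5 gives 1.70 (power 38.9%) at ρ = 0.5 and 2.69 (75.6%) at ρ = 0.8.

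**3. Literal interaction, 2-df test.** This is Hotelling's T² on the within-subject differences, referred to F with 2 and 72 df. Under these assumptions the noncentrality is (50 × 25 / 75) × Σ(gap − mean gap)² / (36(1 − ρ)). Example: gaps 2.5, 3.75, 5 have a sum of squares of 3.125, giving 16.67 × 3.125 / 18 = 2.89 (power 30.0%) at ρ = 0.5 and 16.67 × 3.125 / 7.2 = 7.23 (65.1%) at ρ = 0.8.

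**4. Results.** Each cell gives ρ = 0.5 / ρ = 0.8.

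| Arm gap at Week 4, Week 8, end | 2-df interaction | Last minus first | Arm difference at end |
|---|---|---|---|
| 5, 5, 5 | 5.0% / 5.0% | 5.0% / 5.0% | 91.9% |
| 4, 4.5, 5 | 8.5% / 14.3% | 10.3% / 18.6% | 91.9% |
| 2.5, 3.75, 5 | 30.0% / 65.1% | 38.9% / 75.6% | 91.9% |
| 0, 2.5, 5 | 85.6% / 99.8% | 91.9% / >99.9% | 91.9% |
| 5, 2.5, 0 | 85.6% / 99.8% | 91.9% / >99.9% | 5.0% |

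Simulation of the 2-df and end-of-study tests agreed to within about one percentage point.

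**5. Growth needed for the stated power.** For the last-minus-first contrast to reach 91.9%, the gap must grow by 5/6 of the SD of change: 5/6 × 6.00 = 5.0 points at ρ = 0.5, or 5/6 × 3.79 = 3.2 points at ρ = 0.8. Section 9.4 gives no time profile for its 5-point difference, so it does not support 92% for this test.

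**The case against.** The strongest reply is that the intended meaning can be recovered. The paragraph opens by asking about the percentage at treatment end, and in an arm-by-categorical-time model the arm difference at a named time is itself a contrast built from the arm and interaction coefficients. Because the endpoint accumulates from Day 0, the end-of-study value is also the whole-period percentage. Section 9.4, the opening of 9.6.1 and its closing note therefore all point to the same quantity, and on that reading power is 91.9% in every profile where the final gap is 5 points. This is a fair account of probable intent. It does not cure the sentence, which names an interaction and gives no time points, reference level or linear combination.

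Other points also have some force:

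- The general 0.05 threshold in section 9.6 could be applied to the arm coefficient. What is missing is any statement that this is the primary test.
- The SAP has precedence and may define the contrast. Section 9.6 requires it only to be final before database lock, and the trial is open-label, so the protocol should not leave the choice open until then.
- The intermediate powers are illustrative. Cumulative percentages over 4 weeks and over many months need not share an SD or a common correlation, and some subjects will not have three values. The result for a constant gap (5%) and the 91.9% do not depend on the correlation.
- Several secondary outcomes have their own named tests in 9.6.2, so the carry-over is limited to those that rely on the analogous model.
- The trial is a pilot, and objective 1.2.2 is largely one of estimation. The protocol nevertheless sets an alpha, a power and a significance rule for this endpoint.

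**Conclusion.** The concern holds, and the sentence is wrong as written. The sample-size figure is correct, but the decision rule does not name the test that was sized. Taken literally, the rule has a 5% chance of declaring a constant 5-point advantage, against 91.9% for the arm difference. It can also declare an effect when no difference remains at the end. The size of the loss between those extremes depends on the time profile of the gap and on the assumed SD and correlation: 9% to 19% when the gap goes from 4 to 5 points, 30% to 76% when it goes from 2.5 to 5. If the contrast was meant as the arm difference at end of study, no power is lost, but the text must say so. Because this sentence decides the Phase 2 conclusion, it must be fixed.

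**What to change.** Replace the decision sentence in 9.6.1 with:

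> *A significant treatment effect will be concluded if the two-sided p-value for the treatment-arm coefficient in the regression of the whole-Phase-2 percentage of witnessed doses is ≤ 0.05.*

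This tests the arm difference sized in 9.4, using the regression already described at the end of 9.6.1. If covariates enter that regression as 9.6.1 allows, it is the adjusted form of the t-test. It also uses every subject with a Phase 2 percentage. Section 3.5 allows a minimum of 4 weeks in Phase 2, and a subject with only that has a single value, because Week 4 is also end of study. Such a subject says nothing about change over time but still counts in the whole-period comparison.

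Keep the time-by-arm mixed model as a secondary description of change over follow-up. If the authors prefer to keep it as primary, defining the contrast explicitly as the arm difference at end of study would also remove the ambiguity.

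Put the same wording in the SAP, and state in 9.6.2 which term is tested for secondary outcomes that use the analogous model. The cost is one sentence in 9.6.1, matching SAP text and one clause in 9.6.2, with no new data or patients.
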